DMV	Department of Motor Vehicles
DSM-5	Diagnostic and Statistical Manual of Mental Disorders (Version 5)
DSMB	Data and Safety Monitoring Board
eCRF	Electronic Case Report Form
EEG	Electroencephalogram
EMG	Electromyography
EOG	Electrooculography
FDA	Food and Drug Administration
FDI	First Dorsal Interosseous
GCP	Good Clinical Practice
GTT	Glucose Tolerance Test
Hz	Hertz
ICF	Informed Consent Form
ICH	International Conference on Harmonization
IDE	Investigational Device Exemption
IRI	Interpersonal Reactivity Index
NAMI	National Alliance on Mental Illness
NIH	National Institutes of Health
NIMH	National Institute of Mental Health
NORC	Nutrition Obesity Research Center
OHRE	Office of Human Research Ethics
OHRP	Office for Human Research Protections
PHI	Protected Health Information
PI	Principal Investigator
PMA	Premarket Approval
SMC	Safety Monitoring Committee
SPI	Serial Peripheral Interface
SOP	Standard Operating Procedure
TEP	TMS-evoked potential
TMS	Transcranial Magnetic Stimulation
UE	Unexpected Event
UNC	University of North Carolina
UNC-CH	University of North Carolina at Chapel Hill
US	United States

STUDY SUMMARY	
Title	Modulation of motor cortex excitability by glucose administration
Short Title	Glucose
Protocol Number	19-1451
Phase	Pilot
Methodology	Single-site
Study Duration	This study is expected to last 1 year.
Study Center(s)	This is a single-site study performed at The University of North Carolina at Chapel Hill.
Objectives (Purpose)	Purpose of this pilot study is to investigate how changes in blood glucose level modulates neuronal excitability and brain network dynamics.
Number of Subjects	20
Diagnosis and Main Inclusion Criteria	Eligible participants will be healthy individual without any severe illness and mental disorder.
Description of Intervention (Procedures/methods)	Each participant will be seated in a reclining chair and receive transcranial magnetic stimulation (TMS) to determine resting motor threshold (RMT). At baseline, participants will receive 10 TMS pulses (120% intensity relative to RMT) while wearing an electroencephalography (EEG) net to record brain activity on the scalp. TMS-induced motor-evoked potentials (MEPs) and EEG data will be recorded. In addition, blood glucose level testing will be performed by finger prick to measure baseline glucose level. In an intervention step, glucose drink (75g of sugar) or drinking water (control condition) will be administered. Both blood glucose level testing and TMS-induced MEPs and EEG data collection will be performed at 0, 30, 60, 120, and 180 minutes after drink administration.
Related IRB Applications	17-0149

1.2 INSTITUTIONS

The University of North Carolina at Chapel Hill

1.4 FUNDING SOURCES

Please list below the funding sources for this project:

Sponsor Name	UNC Ramses Number	Sponsor Type	Prime Sponsor Name	Prime Sponsor Type	Sponsor/Grant Number
UNC NORC			NIH/NIDDK	Federal	P30 DK056350

External Funding: This project is externally funded and UNC-CH is the direct recipient of federal funds.

UNC-CH Funding: This project is funded through UNC-CH Nutrition Obesity Research Center.

Classified: This project is not classified.

2 INTRODUCTION

This document is a protocol for a human research study. This study is to be conducted according to U.S. and international standards of Good Clinical Practice (FDA Title 21 Part 312 and International Conference on Harmonization guidelines), applicable government regulations and Institutional research policies and procedures.

2.1 BACKGROUND

More than a third of the adult US population has impaired glucose tolerance, which is tightly linked to obesity and a risk factor for the development of diabetes and disorders of the central nervous system. In particular, diabetes exhibits a bidirectional causal association with depression. A growing literature delineates the pathophysiology underlying mood disorders at the level of large-scale activity patterns in brain circuits (Davidson, 1985; Nusslock et al., 2015; Smart et al., 2015; Sutton and Davidson, 1997), which has enabled the development of novel brain stimulation treatments such as transcranial magnetic stimulation (TMS) (George et al., 1995). TMS is one of the non-invasive brain stimulation tools used to deliver electrical stimuli through the scalp in humans. In general, single-pulse TMS (including paired-pulse TMS) is used to explore brain functioning. TMS on the motor cortex leads to a twitch in the target muscle evoking motor-evoked potentials (MEPs) on electromyography (EMG) electrodes. The MEP is usually used to assess corticospinal tract excitability (Tofts, 1990). In addition, combining TMS with electroencephalography (EEG) can capture cortical excitability beyond corticospinal excitability since EEG mainly captures neural activity of cortical neurons (Farzan et al., 2016). The concurrent combination of TMS with EEG can be a powerful technology for characterizing and modulating brain networks.

2.2 DOSE RATIONALE

In this study, our primary purpose is to investigate how changes in blood glucose level affect neuronal excitability. We will administer a 75g load of glucose (oral glucose tolerance test, OGTT) that complies with the standard guidelines for diagnosing diabetes

2.3 STUDY AIMS/HYPOTHESES

2.3.1 SPECIFIC AIMS

Aim 1. Examine how glucose levels gate neuronal excitability measured by the response to TMS.

Aim 2. Delineate how brain network dynamics are modulated by experimentally induced elevated blood glucose levels.

2.3.2 RESEARCH HYPOTHESES

We hypothesize that glucose administration modulates neuronal excitability measured by TMS-induced MEPs and TEPs. We also hypothesize that frontal theta (4-8Hz) and left frontal alpha (8-12Hz) oscillations, which represent an engaged (theta) and disengaged (alpha) cortical state, are modulated in response to glucose administration compared to water drink. The modulation of neuronal excitability and brain network dynamics is depending on blood glucose level

3 SUBJECT SELECTION AND WITHDRAWAL

A total of 20 healthy participants will be recruited for this study and all data will be collected at UNC-CH. No specific plans have been made to enroll participants from vulnerable populations.

3.1 INCLUSION CRITERIA

In order to be eligible to participate in this study, a participant must meet all of the following criteria:

- Between the ages of 35 and 65
- Right-handed
- Body mass index (BMI) < 30
- Fasting blood glucose test level < 95 mg/dL
- Capacity to understand all relevant risks and potential benefits of the study (informed consent)
- Willing to comply with all study procedures and be available for the duration of the study
- Speak and understand English

3.2 EXCLUSION CRITERIA

A potential participant who meets any of the following criteria will be excluded from participation in the study:

- Diagnosis of diabetes or pre-diabetes
- Neurological disorders and conditions, including, but not limited to:
 - History of epilepsy
 - Seizures (except childhood febrile seizures and ECT-induced seizures)
 - Dementia
 - History of stroke
 - Parkinson's disease
 - Multiple sclerosis
 - Cerebral aneurysm
 - Brain tumors
- Medical or neurological illness or treatment for a medical disorder that could interfere with study participation (e.g., unstable cardiac disease, HIV/AIDS, malignancy, liver or renal impairment)
- Prior concussion
- Prior brain surgery
- Any brain devices/implants, including cochlear implants and aneurysm clips
- Traumatic brain injury
- Anything that, in the opinion of the investigator, would place the participant at increased risk or preclude the participant's full compliance with or completion of the study

Justifications for any exclusions based on race, gender, or ethnicity: Non-English speaking individuals are excluded because the ability to accurately and completely communicate study information, answer questions about the study, and obtain consent are necessary.

Justification for excluding women or women who become pregnant

Pregnant participants will be excluded despite the fact that theoretical risk to mother or fetus is exceedingly small, since no safety data for pregnancy is known to exist for TMS studies. Furthermore, the TMS device description indicates that the device should not be applied to the head, neck, or abdomen of pregnant women. We will verify pregnancy status via a urine pregnancy test for all female participants prior to receiving treatment on the first session of the study. Women will be asked prior to each test sessions about the likelihood they could be pregnant. Any woman who indicates there may be a possibility or is unsure will be reminded the testing is contraindicated in pregnant women and will be offered the opportunity to have pregnancy testing repeated prior to TMS.

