4 BASIC STUDY DESIGN

Participants who pass an initial screening by phone are asked to attend a screening visit where consent is provided, eligibility for study participation is confirmed and demographic information is collected. Participants who are eligible to participate will then be asked to return for two study sessions after an MRI scan. Sessions will start at 8.00 am and study participants will be asked to fast for the preceding 12 hours and to consume approximately 150g of carbohydrates each day for the 3 days prior to the session. The study procedures are identical for both study visits. The order of the two sessions is equally randomized across participants.

In one visit, an oral 3-hour GTT with a 75g load of glucose will be administered. In the other visit, pure drinking water will be used. Both study visits have the following time-line:

1. Determined the target (hand area of the left precentral gyrus, left primary motor cortex) based on MR images using a TMS neuro-navigation system.
2. Fitting of an EEG electrode net.
3. Baseline EEG and MEP measurements elicited by TMS
4. Measurement of fasting blood glucose level by finger prick
5. Administration of drink (glucose drink or water, 296mL of H₂O for both drinks)
6. Capillary blood draw (finger prick) for glucose level testing and TMS-induced EEG and MEP measurements at 0, 30, 60, 120, 180 minutes after drink administration
7. Digitization of EEG electrodes on the scalp using a camera-type scanner

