Single-pulse TMS on the motor cortex leads to a twitch in the target muscle evoking a motor-evoked potential (MEP) measured by electromyography (EMG) electrodes. Participants will be seated in a comfortable armchair with their hands positioned on the armrest. Two disposable electrodes (15x21mm, Ambu Neuroline) will be placed in a tendon-belly arrangement over the first dorsal interosseous muscle and a ground electrode will be placed over the styloid process of the ulna. A figure-eight coil (C-B60, MagVenture) will be used for stimulation and EMG signals will be recorded by an amplifier (MagPro X100, MagVenture). The coil will be placed tangentially over the scalp with the handle pointing backwards and laterally at 45° from the mid-sagittal line. Biphasic TMS pulses will be applied over the motor cortex and the resting motor threshold (RMT) will be defined by the minimum TMS intensity required to evoke MEP of at least 50 uV in 50% of 10 consecutive trials. At baseline, 10 TMS pulses will be applied on the scalp and EEG and EMG data will be collected. At the same time, blood glucose level will be measured by 5uL of finger prick blood sampling as a baseline glucose level. In an intervention step, we will administer a 75g load of glucose drink or drinking water at each study visit. After then, glucose level testing and EMG/EEG data collection will be performed at 0, 30, 60, 120, and 180 minutes after the drink administration. Once participants complete the first study visit, a study coordinator will schedule their next visit with at least 3-day gap.

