6 STUDY PROCEDURES/EVALUATIONS

6.1 SELF-REPORT MEASURES

Study coordinators will consider using a standard safety questionnaire to screen TMS candidates. The following questions represent the basic information required. Additional information may change according to particular demands. Consensus has been reached for this questionnaire (Rossi et al., 2009).

1. Did you ever have a concussion?
2. Do you have or have you ever had diabetes?
3. Do you have or have you ever had anorexia?
4. Do you have or have you ever had OCD?
5. Do you have or have you ever had ADHD?
6. Have you ever had a fainting spell or syncope? If yes, please describe in which occasion(s)
7. Have you ever had severe (i.e., followed by loss of consciousness) head trauma?
8. Do you have any hearing problems or ringing in your ears?
9. Are you pregnant or is there any chance that you might be?
10. Do you have metal in the brain/skull (except titanium)? (e.g., splinters, fragments, clips, etc.)
11. Do you have cochlear implants?
12. Do you have an implanted neurostimulator? (e.g., DBS, epidural/subdural, VNS)
13. Do you have a cardiac pacemaker or intracardiac lines or metal in your body?
14. Do you have a medication infusion device?
15. Are you taking any medications? (Please list)
16. Did you ever have a surgical procedures to your spinal cord?
17. Do you have any disorder related to spinal cord or ventricle?
18. Did you ever undergo TMS in the past?

We will ask these questions in order to follow the standard safety guidelines for TMS studies. Answers from the questions will help us to exclude study participants regarding the safety of TMS

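### At the second session a woman who may be pregnant is only offered a repeat test, and no written rule withholds TMS if she declines

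*Combined protocol and SAP*

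**What the plan says.** Section 3.2 states the exclusion directly: "Pregnant participants will be excluded despite the fact that theoretical risk to mother or fetus is exceedingly small". It gives two reasons: safety data for TMS in pregnancy are lacking, and the device description says that "the device should not be applied to the head, neck, or abdomen of pregnant women".

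The same paragraph sets up two checks:

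- **Urine test.** It is compulsory for all women, "prior to receiving treatment on the first session of the study".
- **Verbal question.** Women are asked before every session how likely a pregnancy is. One who thinks it possible, or is not sure, is reminded of the contraindication and "will be offered the opportunity to have pregnancy testing repeated prior to TMS".

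Three other sections bear on the point:

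- **Section 9.3.1** discontinues a participant who meets an exclusion criterion, including one that has newly arisen. It also allows discontinuation when the investigator sees increased risk.
- **Section 6.1** lists a safety question about current or possible pregnancy, introduced by "Study coordinators will consider using a standard safety questionnaire to screen TMS candidates".
- **Section 5.2** provides that after the first study visit "a study coordinator will schedule their next visit with at least 3-day gap". A minimum gap is given, with no maximum.

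**The concern.** The verbal question exists to detect uncertainty about pregnancy before stimulation. Once a woman has voiced that uncertainty, her answer should decide whether TMS goes ahead. As written it leads to a reminder and an offer, and an offer can be declined. The plan is then strict at the first session, where every woman is tested whatever she says, and optional at the second, where a woman may just have said she could be pregnant.

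What is at stake is consistent application of an exclusion that the plan itself adopted. Section 8.1 says participants gain no direct benefit, so there is nothing on the other side to set against an avoidable exposure. Section 12.4 gives eligibility review and device administration to the coordinator and research assistants, who would be better served by a fixed rule than by having to decide at the visit.

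**Working it through.** The plan gives no figure on this point and none is needed. The check is to follow each possible case and ask which written rule decides whether TMS is given.

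1. **First session, any woman.** The urine test is compulsory before treatment. A positive result excludes her. The rule is complete.
2. **Second session, she reports no chance of pregnancy.** No test is called for and TMS proceeds on self-report. This is a design choice and is not the point raised here.
3. **Second session, she is unsure, accepts the test, and it is negative.** TMS proceeds with her status resolved.
4. **Second session, she is unsure, accepts the test, and it is positive.** The section 3.2 exclusion applies and section 9.3.1 discontinues her. This takes pregnancy to be an exclusion criterion although it stands in the justification paragraph and not in the bulleted list, which is the natural reading.
5. **Second session, she is unsure and declines the test.** Section 3.2 is silent.

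Case 5 is the gap. The provisions that might close it are these:

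- **Section 9.3.1, exclusion criterion met.** The criterion is pregnancy. An untested possibility does not clearly meet it.
- **Section 9.3.1 and the last bullet of section 3.2, investigator's opinion.** These permit a stop but do not require one.
- **Section 6.1 questionnaire.** Its use is to be considered, it is framed as a screen of candidates for TMS, and its answers are said to help with exclusion. No answer triggers withholding.
- **Section 3.1, willingness to comply with study procedures.** A test that is only offered is not a procedure she has refused to comply with.
- **Section 9.4, stopping rules.** These cover drop-out, seizures and outside evidence of harm. Pregnancy is not mentioned.
- **Appendix E, telephone script.** It has no pregnancy question.

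Two procedure lists are also silent, but little weight belongs on that. Section 4 introduces its steps with "Both study visits have the following time-line" and names no pregnancy check, yet it also leaves out the questionnaires and cognitive task that section 5.2 places in the visits. The schedule in Appendix A has no pregnancy-test row, yet it also omits the MRI scan. Both lists show only that the rule is not stated there.

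On scale, the protocol enrols 20 participants, with the age criterion "Between the ages of 35 and 65", and one of the two TMS sessions is affected. The number of women, and how often status would be uncertain, are not given. A ceiling on repeat tests is 20 participants × 1 session = 20, reached only if every participant were a woman and every one were unsure. The real number would be far smaller.

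**The case against.** The strongest reply is that the plan already does most of the work. It excludes pregnancy, cites the device warning, tests every woman at the first session, asks again before each session, gives a reminder, makes a test available before TMS, and lets the investigator stop. Harm through the remaining gap needs several things together: a woman voices doubt, she declines a test straight after the reminder, staff go ahead anyway, and she is in fact pregnant. The paragraph's evident purpose is to keep pregnant women from being stimulated, so staff applying it sensibly would probably hold back. The protocol also rates the theoretical risk as very small.

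Most of this stands, and it sets the weight of the point. It does not remove the gap: the protection in case 5 rests on what staff would probably do, and the plan chose to exclude pregnancy despite the small risk.

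A second objection also stands. The proposed change acts only on women who volunteer doubt. A woman who reports no chance of pregnancy remains untested at the second session, however long after the first it falls. Status at that visit would still rest on self-report.

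A reader might go further and infer that the plan allows TMS in women known to be pregnant, or tells staff to proceed after a refusal. The documents support neither. Established pregnancy leads to discontinuation, and the text after a declined offer is silent; it gives no instruction to stimulate. Nor should the point be tied to sample size or power. The data-discard sentence in section 9.4 concerns participants who drop out because of the glucose load or discomfort with stimulation, and declining a pregnancy test is neither.

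**Conclusion.** The gap is real and narrow. At the second session, when a woman's pregnancy status is uncertain and she declines the repeat test, no visible sentence withholds TMS, and the existing backstops need either an established pregnancy or an investigator's judgement. It is a minor patient-safety point with a near-costless remedy. It has no claimed bearing on estimates, error rates or conclusions.

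The conclusion rests on the visible text. Consent pages and some appendix pages were not available, and a withholding rule could be stated there. That the path is rare is a judgement from the small sample, the age range and the events that must coincide; the documents give no frequency.

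**What to change.** In section 3.2, replace the offer of a repeat test with a requirement. For a woman who reports possible or uncertain pregnancy, the sentence would end: *must have a negative repeat urine pregnancy test before TMS in that session; if she declines, TMS is withheld and the session may be rescheduled; if she tests positive, she is discontinued under section 9.3.1.*

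Rescheduling fits the plan, which sets only a minimum of 3 days between sessions. The cost is one sentence, an occasional extra urine test of a kind the trial already runs, and now and then a delayed or lost second session.

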3.3 STRATEGIES FOR RECRUITMENT AND RETENTION

3.3.1 RECRUITMENT

We intend to recruit 20 healthy participants at the University of North Carolina at Chapel Hill. Study coordinator will be informed of the inclusion and exclusion criteria and will be asked to discuss the study with their subjects. Study coordinator will identify subjects they believe to be appropriate for this study based on the information we will provide them about the study. Study coordinator will ask subjects whether they are willing to be contacted by the research team regarding participation.

3.3.2 RETENTION

Our retention strategy includes monetary compensation for the time and effort required to participate in the study. The participant will receive payment at the stimulation session. The research staff will also give each participant a reminder call or email for the stimulation session. Each research staff member will be easily available for the participants to contact via email or phone.

[figure not shown]
The inclusion criteria state that each participant must be able to understand all risks and benefits associated with this study. We will be asking each participant to answer questions about the consent form to determine that the study process and the duration of participation are completely understood by all participants. We will aim to have a specific research team member assigned to complete all sessions with the same participant to establish rapport and encourage the participant to continue attending sessions.

4 BASIC STUDY DESIGN

Participants who pass an initial screening by phone are asked to attend a screening visit where consent is provided, eligibility for study participation is confirmed and demographic information is collected. Participants who are eligible to participate will then be asked to return for two study sessions after an MRI scan. Sessions will start at 8.00 am and study participants will be asked to fast for the preceding 12 hours and to consume approximately 150g of carbohydrates each day for the 3 days prior to the session. The study procedures are identical for both study visits. The order of the two sessions is equally randomized across participants.

In one visit, an oral 3-hour GTT with a 75g load of glucose will be administered. In the other visit, pure drinking water will be used. Both study visits have the following time-line:

1. Determined the target (hand area of the left precentral gyrus, left primary motor cortex) based on MR images using a TMS neuro-navigation system.
2. Fitting of an EEG electrode net.
3. Baseline EEG and MEP measurements elicited by TMS
4. Measurement of fasting blood glucose level by finger prick
5. Administration of drink (glucose drink or water, 296mL of H₂O for both drinks)
6. Capillary blood draw (finger prick) for glucose level testing and TMS-induced EEG and MEP measurements at 0, 30, 60, 120, 180 minutes after drink administration
7. Digitization of EEG electrodes on the scalp using a camera-type scanner

